# **Study Overview**

## **Data Analysis Aims:**

1. Demonstrate that Unified Protocol (UP) treatment reduces alcohol consumption relative to Take Control (TC), as measured by our primary outcome measure, mean number of drinks consumed per week.

Comparisons will be made for data obtained for the treatment period for the two conditions. Specifically, the hypothesis that participants in the UP condition will evidence greater reductions in our primary efficacy measure (mean weekly number of standard drinks) than participants receiving TC will be examined using conditional latent growth models (LGM), modeled using MPlus 7.0 (Muthén & Muthén, 1998-2012). Research personnel will examine changes in the weekly mean number of drinks consumed per day over the course of treatment (i.e., study sessions 1 to 16). They will also examine whether the proportion of subjects achieving safe levels of drinking (males = 2 drinks per day; females = 1 drink per day) is significantly greater in the UP condition than in the TC group (guidelines from USDA, 2010). This will be done by calculating odds ratio effect sizes (with 95% confidence interval) contrasting safe levels of drinking in the UP vs. TC groups.

2. Demonstrate that the UP, relative to TC, reduces alcohol intake on other measures of alcohol consumption and evaluate the extent to which this also leads to a comparative decrease in measures of craving.

Conditional LGM will be used to test the hypothesis that UP will both demonstrate greater reductions in the secondary efficacy measures of percent days heavy drinking per week (defined as more than 3 drinks per drinking day for biological women and more than 4 drinks per drinking day for biological men [NIAAA guidelines]), percent days of drinking per week, and in alcohol craving (as assessed by the Alcohol Urge Questionnaire and the Obsessive Compulsive drinking scale) than the TC condition.

3. Demonstrate that the UP results in greater reductions in anxiety and depression as measured by the SIGH-A, SIGH-D, ODSIS, and OASIS than TC, and that there will be a correlation between these reductions and the decreases seen in mean weekly number of standard drinks consumed per day, percent days heavy drinking per week, percent days drinking per week, and alcohol craving.

This will be examined using conditional and parallel-process LGC. Research personnel will first conduct separate LGM for anxiety and depression. Then they will conduct a series of parallel process LGM to examine how changes in anxiety and depression relate to changes in the primary and three secondary alcohol outcomes. Separate parallel process LGM will be conducted for

each alcohol outcome, and both anxiety and depression will be included in each parallel process LGM.

4. Demonstrate that the UP results in greater changes in temperament (e.g., reductions in neuroticism) and emotion regulation (e.g., experiential avoidance) variables associated with anxiety and depression than TC, and that these changes are associated with changes in anxiety and depression.

This will be examined using LGM models similar to those described above. These parallel process LGM will not provide formal tests of mechanisms of change as these models will examine concurrent changes. If the results from these models are promising, they will be followed by models that permit more fine-grained examinations of temporal dependencies of change.

5. Demonstrate that the UP will reduce impulsive and risk-taking behaviors. Our working hypothesis is that the UP will decrease risk taking behavior as assessed using the Cambridge Gambling Task and the Balloon Analog Risk Task, and impulsivity as measured by the Go/NoGo and the Continuous Performance Test (CPT).

Repeated measures mixed models analysis will be used to analyze data obtained for prerandomization and week 16 data for the Cambridge Gambling Task, the Balloon Analog Risk Task, the Go/NoGoTask, the CPT, and Go/No Go. Model generated group least square means values for week 16 will be compared using student t-tests.

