# Table 1. Visit Projection Table

#### **Subjects**

A total of 60 participants will be enrolled, with a target male to female ratio of 33:27. This ratio reflects the higher prevalence rates of AUDs in biological men compared to biological women. Forty participants will be randomized to the UP condition and 20 to the Take Control condition. In addition, 25 participants from the UP group will receive two fMRI scans (pre- and post-treatment).

Participants will be recruited via flyers, brochures, lab website and StAR Facebook page, MBTA advertisements, etc. Telephone screenings will determine initial eligibility, and potential research participants will be invited to CARD, located at Boston University, for a more extensive assessment of alcohol use and emotional disorders.

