#### **Inclusion/ Exclusion Criteria**

# **Inclusion Criteria:**

- 1) DSM-5 diagnosis of an alcohol use disorder (AUD)
- 2) DSM-5 diagnosis of Social Anxiety Disorder (SAD), Panic Disorder/Agoraphobia (PD/A), Generalized Anxiety Disorder (GAD), and/or Obsessive Compulsive Disorder (OCD) as determined by a clinician-administered diagnostic assessment using the Anxiety Disorder Interview Schedule for DSM-5 (ADIS-5). Clinically significant diagnoses will be determined by assignment of an ADIS clinical severity rating (CSR) of 4 (definitely disturbing/disabling on the 0-8 CSR scale) or higher on at least the principal diagnosis
- 3) Adults 21 years or older
- 4) Expressed desire to stop drinking alcohol completely or to reduce alcohol consumption
- 5) Reported drinking an average of at least 15 standard drinks per week for males, or 8 for females occurring over a 28-consecutive day period during the 90 day-long time window that preceded the screening session
- 6) Must be willing to discontinue any form of psychotherapy, except AA, for either anxiety or depression prior to screening

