Next, the RA will take the participant to a UP treatment room. The RA will then conduct the Alcohol Timeline Follow-Back assessment with the participant. The RA will need to collect drinking data for the past 90 days. Then, the RA will download the RealLife Exp application on the participants' phone to activate the EMA component of the study. The survey should be activated on the screening session. Seven days after the screening session the RA should email the participant to deactivate the survey (see EMA procedures for more information). We cannot deactivate the survey pack remotely, which is why the participant needs to be instructed on when and how to do so. Deactivating the survey pack will only stop notifications from being sent to the participant during non-EMA weeks, it will not delete the account.

The RA will give the participant the EMA instructions handout and the "What is AUD" handout to take home, both of which can be found in the Screening tab of the participant binder. The RA then loads the Screening Self-report Qualtrics survey on the study computer in room 233D for the participant. All surveys are set up to ensure that participants answer every question, eliminating the possibility of blank responses. However, the RA must ensure the participant has reached the last page of the survey before moving on to the next portion of the session. Upon completion of the questionnaires, the participant notifies the RA and may take a break. The RA notifies the IE that the participant is ready for the assessment and emails the link to the IE assessment survey, which includes the ADIS, SIGH-A, and SIGH-D. Alternatively, the IE can access all assessment surveys through Qualtrics. When the IE finishes the assessment, he/she will alert the RA that the assessment is complete. The RA will thank the participant for his/her time, and inform the participant that he/she will receive a phone call about eligibility in the next 1-2 weeks after the team has established consensus for study enrollment.

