#### Randomization

Prior to the start of the trial, a random number generator was used to establish a randomization schedule that assigns participants to either the active treatment (UP) or comparison condition (TC). Once a new participant is enrolled in the trial, the RA will refer to the next assignment in the randomization schedule

The current trial aims to recruit 40 participants in the UP condition and 20 participants in the TC condition.

Once the participant is randomized, the RA will contact the participant to discuss scheduling and provide further information about length of the trial. TC participants will complete 12 sessions of therapy (in a maximum of 16 weeks), while UP participants will complete 16 weeks of therapy (in a maximum of 21 weeks). Additionally, follow-up assessments will be completed at one month and six months posttreatment.

If the participant is randomized to TC, the next session is session 1, and the RA will schedule the session based on the participant's and assigned therapist's availability. If the participant is randomized to the UP condition, the RA will potentially schedule the participant

for the fMRI session prior to scheduling session 1 with the therapist. The first study session will be scheduled within 4-weeks after the in-clinic baseline assessment. If the one-month window expires before the participant can complete the first session, then the assessment must be repeated to assess the participant's continued eligibility for the study (a "refresher").

To schedule an fMRI session, the RAs will need to refer to the CILSE scheduling calendar to confirm that the scanner and the MRI technicians are available and to book the appointment. The RA will need to book 30 minutes in the

Med Lab at CARD for the urine, drug, and/or pregnancy test, and 1.5 hours at CILSE for the scan. Once appointments are scheduled, the RA will document the time and date for all involved study staff in Titanium (see How to Log a Treatment Session in Titanium).

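### Aim 1's safe-drinking odds ratio specifies no adjustment for baseline drinking, which would add power and sharpen the marginal effect if baseline is at least moderately prognostic

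*Combined protocol and SAP*

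**What the plan says.** The Data Analysis Aims section (Aim 1) makes a conditional latent growth model of mean weekly drinks the primary test. It then adds a responder comparison, the proportion "achieving safe levels of drinking (males = 2 drinks per day; females = 1 drink per day"), and asks whether this "is significantly greater in the UP condition than in the TC group". The stated method is "calculating odds ratio effect sizes (with 95% confidence interval) contrasting safe levels of drinking in the UP vs. TC groups". No covariate, regression model or alpha is given for this comparison; the 95% interval implies a two-sided 5% level.

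Four other places bear on it:

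- **Inclusion Criteria, item 5:** "Reported drinking an average of at least 15 standard drinks per week for males, or 8 for females", over 28 consecutive days within the 90 days before screening. No upper limit on drinking is listed.
- **Informed Consent/Screening Session:** "The RA will need to collect drinking data for the past 90 days", by Timeline Follow-Back (TLFB), before randomization.
- **Subjects:** "A total of 60 participants will be enrolled, with a target male to female ratio of 33:27", and "Forty participants will be randomized to the UP condition and 20 to the Take Control condition".
- **Randomization:** "a random number generator was used to establish a randomization schedule". No stratification is described.

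**The concern.** The endpoint dichotomizes drinking at a fixed level, while participants start at very different distances above it. A man entering at 15 drinks a week responds by dropping one drink; a man entering at 60 (an illustrative figure) must drop 46. Baseline drinking is therefore a plausible predictor of response. It is measured on the scale of the threshold, costs nothing further to collect, and is not balanced by any design feature described.

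If baseline is prognostic, a two-group contrast leaves that variation in the noise. With 20 participants in the smaller arm, the lost power could matter to whether a real difference is detected. Leaving adjustment unspecified also leaves room to choose between adjusted and unadjusted results after the data are seen.

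**Working it through.** **No figure to reproduce.** The documents give no power, response rate or effect size for this endpoint. The response rates and correlations below are assumptions.

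**Inputs from the documents.** Thresholds: 2 × 7 = 14 and 1 × 7 = 7 drinks a week. Entry relative to threshold: 15/14 = 1.07 (men) and 8/7 = 1.14 (women). Arms: 40 and 20. Men: 33/60 = 55%.

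**Step 1: the unadjusted odds ratio.** SE(log OR) = √(1/a + 1/b + 1/c + 1/d), with expected cell counts.

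- 20% v 50%: TC 4/16, UP 20/20. OR = 1/0.25 = 4.00. SE = √(0.25 + 0.0625 + 0.05 + 0.05) = 0.642. 95% CI 1.14 to 14.09.
- 30% v 60%: TC 6/14, UP 24/16. OR = 1.5/0.4286 = 3.50. SE = √(0.1667 + 0.0714 + 0.0417 + 0.0625) = 0.585. 95% CI 1.11 to 11.02.

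Power = Φ{[d − 1.96√(p̄q̄(1/20 + 1/40))] / √(p₁q₁/20 + p₂q₂/40)}, where d is the difference in proportions.

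- 20% v 50%: (0.30 − 0.263)/0.119 = 0.31, so power is 62%.
- 30% v 60%: (0.30 − 0.268)/0.128 = 0.25, so power is 60%.

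**Step 2: the effect of adjustment.** The check simulated 3,000 trials of 40:20 per setting, with 55% men and log baseline drinks above the sex-specific threshold. The within-arm correlation r between baseline and post-treatment log drinks (both relative to threshold) was varied, with marginal response rates held fixed. Likelihood-ratio tests compared arm alone with arm plus log baseline drinks and sex. The variance ratio is adjusted over unadjusted, for the risk difference standardized over the sample.

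| r | Power, 20% v 50%: unadjusted → adjusted | Power, 30% v 60%: unadjusted → adjusted | Variance ratio |
|---|---|---|---|
| 0 | 65.3% → 66.1% | 63.4% → 63.2% | 1.03, 1.01 |
| 0.3 | 64.0% → 66.9% | 62.6% → 64.9% | 0.98, 0.96 |
| 0.5 | 64.4% → 70.0% | 61.3% → 68.0% | 0.92, 0.90 |
| 0.7 | 64.0% → 77.7% | 60.4% → 74.1% | 0.82, 0.78 |

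**Step 3: the conditional odds ratio.** At 20% v 50%, the median SE of the arm coefficient (Firth fits) rises from 0.63 unadjusted to 0.67, 0.71 and 0.77 at r = 0.3, 0.5 and 0.7. The log odds ratio itself moves from about 1.33 to 1.40, 1.54 and 1.80. The interval widens, but the estimate moves further from zero, so the test gains power.

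**Step 4: sex.** Adjusting only for the log of baseline over threshold gave power within one percentage point of baseline plus sex in every setting (for example 78.1% v 77.7% at r = 0.7, 20% v 50%). The simulation lets sex act only through the threshold, so this shows that the ratio carries that part of sex. It does not show that sex has no other effect.

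**Step 5: error rate and separation.** With 20% responding in both arms, rejection was 5.4 to 7.3% unadjusted and 6.3 to 8.2% adjusted. Near-separation (a coefficient above 8 in absolute value) occurred in 0 to 4% of trials with a treatment effect and in up to 8% under the null.

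**The case against.** **The unadjusted analysis is valid, and it is not primary.** Both parts stand. Randomization protects the unadjusted contrast, and its simulated null rejection was near nominal. A reader might infer that chance imbalance in baseline drinking makes it biased. Averaged over randomizations it does not; the 5% level already allows for imbalance. The SE of a standardized baseline difference at 40:20 is √(1/40 + 1/20) = 0.274, so a gap of 0.5 SD or more arises in about 7% of trials. In such a trial the unadjusted result is harder to interpret, but that is a conditional statement, not a defect of the test.

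**The plan does not say the odds ratio is crude.** This stands too. An odds ratio with a confidence interval could come from a logistic model. For dropouts, Premature Study Termination points to a data analysis section of the grant that is not among the documents. Only the absence of a specified adjustment can be asserted.

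**Adjustment widens the odds ratio's interval.** This is correct for the conditional odds ratio (Step 3), so one cannot say that the plan gives away precision of the odds ratio as such. The gain is in power and in the precision of a marginal effect.

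**The size of the gain is assumed.** This stands. Distance to the threshold makes baseline plausibly prognostic, but the documents do not show that it is strongly so. Below a moderate correlation there is little to gain, although the power cost of adjusting is also negligible.

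**The 40:20 split.** It costs some precision against 30:30, but that is a separate matter which adjustment does not address.

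**Conclusion.** The point holds as an efficiency and pre-specification gap in a supporting analysis. Aim 1 specifies no covariate adjustment for the safe-drinking comparison, although a pre-randomization measure on the scale of the threshold is available.

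Under assumed rates of 20% v 50% or 30% v 60%, the power forgone is about 0 to 3 points for correlations up to 0.3, 6 to 7 at 0.5 and 14 at 0.7. The variance of the standardized risk difference falls by 8 to 10% at 0.5 and 18 to 22% at 0.7. Baseline drinking relative to the threshold is the covariate that matters. A separate term for sex adds little in these calculations, because entry rule and threshold are both scaled by sex.

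The documents do not support reading this as a biased or invalid analysis, or as a fault in the primary latent growth model.

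**What to change.** Before outcomes are analyzed by arm, specify for the safe-drinking comparison:

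1. **Model.** Logistic regression with arm and the log of baseline TLFB drinks per week divided by the sex-specific threshold (14 or 7). Sex is optional.
2. **Baseline window.** One named pre-randomization TLFB window. The documents use three look-backs: 28 days for entry, 90 days for collection, and two weeks in the exclusion from active treatment.
3. **Estimates.** The standardized (marginal) risk difference and marginal odds ratio, each with a 95% interval by a named method. Keep the crude proportions and crude odds ratio as description.
4. **Separation.** A penalized (Firth-type) fit with a trigger fixed in advance. Correct its intercept before standardizing, because the penalty pulls predicted probabilities toward 0.5.

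The cost is a short paragraph in the plan and modest extra code; no new data are needed. There are small downsides. The conditional odds ratio is a different quantity from the crude one and has a wider interval, which is why the marginal effects should be the reported estimates. The unpenalized adjusted test may run slightly above 5%. The gain is near zero if baseline drinking turns out to be weakly prognostic.

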# fMRI Aims:

1. Demonstrate that the UP will attenuate changes resulting from performance on alcohol-word and negative-word Stroop tasks in the activity of frontal-parietal and midbrain regions and the connectivity to networks associated with these regions in AUD subjects. Our working hypothesis is that midbrain activity will be lower in UP participants than those in the TC condition following performance on alcohol and negative emotion Stroop task, which will occur in association with enhanced mid-brain-frontal connectivity and increased synchrony.

2. Demonstrate that the UP attenuates the enhanced regional brain activity and craving- induced by exposure to alcohol related cues in AUD subjects. Our hypothesis is that exposure to alcoholrelated cues will increase brain activity in select limbic and prefrontal areas to a lesser degree in UP completers as compared to UP participants at baseline.

3. Demonstrate that the UP induced changes in brain activity are predictive of reduced ethanol consumption.

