## **General Contact Information**

# **Staff Personnel Contacts and Locations**

# **Research Design**

In this clinical trial, research personnel will further assess the UP's effectiveness in reducing alcohol consumption in participants with comorbid AUD/AXD. Participants will be randomized to one of two conditions: 1) treatment with the UP or 2) treatment with therapist-guided *Take Control* (TC; a psychoeducation-based, alcohol reduction program developed by NIAAA). In addition, a subset of twenty-five participants (UP condition only) will complete functional magnetic resonance scanning (fMRI) to examine the effects of the UP on changes in

brain activity in areas important to regulation of emotional and reward processes implicated in excessive alcohol consumption.

The primary hypotheses are that the UP compared to TC will: 1) be superior in acute symptom reduction from pre- to post-treatment, and 2) evidence greater reductions in percent days heavy drinking, percent days of drinking per week, and alcohol craving.

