#### **Treatment Conditions and Specifications**

Participants will be assigned to one of two groups: UP or TC. Participants in the UP group may also be asked to undergo two brain MRI scans of less than two hours of duration. The first MRI scan will occur after the participant has been randomized but before the first treatment session, and the second brain MRI scan will occur within a two week window after the last treatment session.

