#### Eligibility

If the participant is not eligible, the RA will contact the participant, and will provide the participant with an appropriate referral if relevant, which can be found in:

If the participant is not satisfied with

the explanation for why they are not eligible, the RA will inform them the PD will contact them to explain further.

If the participant is eligible, they will be randomized into either the UP or TC condition. They will be contacted for scheduling schedule for either session 1 or the baseline MRI (only a subset of UP participants will be contacted about the MRI).

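### fMRI Aim 1 predicts a UP-versus-TC difference in midbrain activity, but only UP participants are scanned, so the contrast cannot be estimated

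*Combined protocol and SAP*

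**What the plan says.** The fMRI Aims section gives Aim 1 the goal "Demonstrate that the UP will attenuate changes resulting from performance on alcohol-word and negative-word Stroop tasks" in frontal-parietal and midbrain regions. It then states a working hypothesis that "midbrain activity will be lower in UP participants than those in the TC condition following performance on alcohol and negative emotion Stroop task", together with stronger midbrain-frontal connectivity and synchrony. Aim 2 opens "Demonstrate that the UP attenuates the enhanced regional brain activity", but its hypothesis is within-arm: UP completers against UP participants at baseline. Aim 3 reads "Demonstrate that the UP induced changes in brain activity are predictive of reduced ethanol consumption".

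The sections on who is scanned all point one way:

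- Research Design: "a subset of twenty-five participants (UP condition only) will complete functional magnetic resonance scanning (fMRI").
- Subjects: "25 participants from the UP group will receive two fMRI scans (pre- and post-treatment").
- Treatment Conditions and Specifications: "Participants in the UP group may also be asked to undergo two brain MRI scans of less than two hours of duration".
- Eligibility: "only a subset of UP participants will be contacted about the MRI".
- Randomization: a TC participant goes directly to session 1, whereas a UP participant may first be booked for a scan.
- fMRI: the component is filled from the UP condition until enough participants have complete scans.
- Instructions for Payment and Compensation Schedule: both scan payments are marked as UP only.

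**The concern.** A hypothesis about a difference between two arms needs measurements in both. Here one arm has none, so this is not a matter of low power: there is no estimate at all. If the sub-study later reports a within-UP change under a hypothesis that names TC, the comparison will have been changed without saying so, and readers may take the result as controlled evidence.

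A related problem runs through all three aims. They say that UP attenuates brain responses or induces changes in them. Without scanned controls, change from the first to the second scan cannot be separated from the passage of time or from the effect of being scanned twice.

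**Working it through.** The plan gives no sample size or power figure for the imaging contrast, so there is none to reproduce. The check has four steps.

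**1. Scanned numbers by arm.** Subjects gives 40 UP and 20 TC, with 25 UP participants scanned twice.

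- UP: 25/40 = 62.5%
- TC: 0/20 = 0%

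The standard error of a UP-minus-TC difference is SD × √(1/n_UP + 1/n_TC). With n_TC = 0 the second term is a division by zero. The contrast is undefined whatever SD or significance level is chosen.

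**2. Could any text that names no arm supply TC data?**

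- *Exclusion Criteria* rules out people with MRI contraindications, and the *fMRI* section requires all enrolled participants to be willing and able to be scanned. Both are entry screens and assign no scan. The *fMRI* section goes on to draw the component from UP.
- *Assessment Measures Administration* marks the Stroop task at baseline and in a last-session column headed for session 12 or 16. That column serves every measure. The Stroop row is labelled as fMRI and carries the note that ties it to the scan, so it gives TC no separate Stroop assessment. A Stroop done outside the scanner would not yield midbrain activity in any case.
- The task descriptions for the MRI component say what is shown in the scanner, not who is scanned beyond those in the component.

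**3. Payment cross-check (Compensation Schedule).**

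- Stated maxima: $450 - $250 = $200 = 2 × $100, the two scans.
- Listed items, UP: 100 + 50 + 75 + 50 + 100 + 100 + 100 = $575.
- Listed items, TC: 50 + 75 + 50 + 100 + 100 = $375.
- Difference from listed items: $575 - $375 = $200.

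The listed items do not add up to the stated maxima. The gap between arms is $200 either way, and only that gap is used here. It leaves no scan payment for TC.

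**4. What the alternatives could detect (illustration only).** Assume two-sided α = 0.05, 80% power and a normal approximation; the plan states none of these for imaging. The multiplier is 1.960 + 0.842 = 2.802.

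- Within UP, 25 pairs: 2.802/√25 = 0.56 SD of the change.
- UP against TC, 25 versus 20 scanned: 2.802 × √(1/25 + 1/20) = 0.84 SD.
- UP against TC, 25 versus 10 scanned: 2.802 × √(1/25 + 1/10) = 1.05 SD.

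The first figure is in SDs of change and the other two are in SDs of a single measurement, so they are not on one scale. The finding does not depend on any of them.

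**The case against.** The strongest reply is that this is one clause of a working hypothesis in a sub-study. Aim 2 is already framed within UP. Aim 3 concerns an association that can be examined within UP, and the attenuation and connectivity parts of Aim 1 can still be described there. The *fMRI* section also refers to aims in an approved study protocol, which may be worded differently. Finally, rewriting a hypothesis after scanning has started carries its own risk of looking post hoc.

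Much of this is fair, and it limits the finding without removing it. The clause is the only one in the fMRI aims that sets UP against TC, and it conflicts with every section that assigns scans. In Aim 3 only the wording that UP induced the changes goes too far. If the approved protocol has different wording, the two texts should be reconciled. The post hoc risk is a reason to date and disclose the change, not to leave an untestable hypothesis in place.

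Three further points deserve attention in the same edit:

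- The Aim 1 hypothesis refers to a negative-emotion Stroop. The description under the MRI component mentions four blocks but names only alcohol, colour and neutral words.
- The *fMRI* section says about half of eligible UP participants will be asked. Half of 40 is 20, not 25.
- Restricting analysis to people with both scans selects those who stayed. Entry also requires high recent drinking, so regression to the mean is a further explanation for change.

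**Conclusion.** The concern holds. The UP-only scanning design is consistent across the document as to arm; the TC comparator in the Aim 1 hypothesis is what conflicts with it. With 25 UP and 0 TC participants planned for scanning, the stated contrast cannot be estimated. This conclusion rests on the text alone and needs no assumed SD, α or power. Under all three aims, pre-to-post change can be described but not attributed to UP. The correction should be made, but its reach is limited to the imaging sub-study: the primary drinking outcome and the clinical comparisons of UP with TC are not affected.

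**What to change.** 1. Remove the TC comparator from the Aim 1 hypothesis and restate it within UP. For example: among UP participants with both scans, midbrain activity after the Stroop task will be lower post-treatment than pre-treatment, accompanied by greater midbrain-frontal connectivity and synchrony. Reconcile the Stroop word types with the task description at the same time.
2. Reword all three aims as change from before to after UP, replacing the statements that UP attenuates or induces the changes.
3. Date and disclose the edit. *Study Procedures* says scans were paused in 2020 and resumed in 2021, so scanning had already begun. Keep the UP-versus-TC hypothesis on record and report it as not testable under the design.
4. State that all fMRI results are uncontrolled, so change cannot be separated from time or repeat-scan effects. Note selection by dropout and regression to the mean as further limits.

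The cost is wording only, with no added scans, and a weaker imaging claim that the design already imposes. Keeping the between-arm hypothesis would instead require TC scans: up to 20 × 1 = 20 for a post-treatment comparison, or up to 20 × 2 = 40 for pre and post.
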